### **Current pain assessment**

Subjects will be asked to record their current CRPS-related pain intensity.

The subjects will be asked to answer the following question:

*“Please rate your pain by selecting the one number that best describes how much pain you have right now.”*

#### **12.3.1.3 Pain intensity question of the PROMIS-29 profile**

At Visit 11, the pain intensity question (question number 29, GLOBAL07) of the PROMIS-29 profile (Section 18.3.4) will be used as 1 of the criteria for continuing into Treatment Period B. At Visit 9 and Visit 10 the PROMIS pain question will be used to monitor efficacy.

The subjects will be asked to answer the following question on an 11-point NRS (0 = no pain, 10 = worst imaginable pain):

*“In the past 7 days, how would you rate your pain on average?”*

#### **12.3.2 Dynamic mechanical allodynia**

Allodynia is defined as pain in response to a non-nociceptive stimulus. In cases of mechanical allodynia, even gentle mechanical stimuli such as a slight bending of hairs can evoke pain. The DMA is assessed by the investigator, documented in the source data, and transferred to the eCRF. A Q-tip fixed to an elastic strip exerting a force of 100 mN (Ziegler et al. 1999) is applied in a single sweeping motion (1 cm to 2 cm length) on the skin of the affected limb.

The subjects are asked to judge the stimulus intensity on an NRS (0 to 10), with “0” in this case meaning “no pain”, while each “pricking”, “stinging” or “burning” sensation is defined as a painful sensation, being evaluated by giving a value greater than “0”. A value of “10” corresponds to the individual maximum pain imaginable. The tactile stimulus is tested 5 times. If the subject reports a value of “10”, then no further test will be performed for the respective visit. The degree of pain sensitivity is calculated by the geometrical mean of the pain ratings given (Maier et al. 2010).

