#### **Dynamic mechanical allodynia**

The change from baseline in the DMA will be analyzed using a similar model as for average pain intensity. Only subjects with allodynia at baseline, i.e., a DMA score greater than 0 on the 0 to 10 NRS, will be included in the analysis.

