#### 1.5.3.4 Confirmatory testing strategy for secondary endpoints

A confirmatory testing procedure will be used for testing of the superiority of neridronic acid 400 mg versus placebo with respect to the primary and selected secondary efficacy endpoints (change from baseline to Week 26 in the average pain intensity, change from baseline to Week 12 in the pain intensity level of DMA, change from baseline to Week 12 in the PPT ratio, and change from baseline to Week 12 in the ratio of figure of eight measurements).

First, the primary endpoint will be tested at a one-sided level  $\alpha = 2.5\%$ . If the first test is statistically significant, the 4 secondary endpoints will be tested in a second stage.

To control for the family-wise type I error rate at the one-sided 2.5% level, a hybrid Hochberg-Hommel step-up procedure (hybrid-0 procedure in Gou et al. 2014) will be applied. The testing procedure uses the ordered p-values  $p_{(1)} \geq p_{(2)} \geq p_{(3)} \geq p_{(4)}$ . At first, if the largest p-value  $p_{(1)} \leq \alpha$ , then all 4 hypotheses are rejected. Otherwise the associated null hypothesis  $H_{(1)}$  is accepted and testing proceeds to the next step. In general, at Step  $i = 2,..,4$ , if  $p_{(i)} \leq c_i\alpha$ , then any hypothesis with p-value  $\leq d_i\alpha$  will be rejected and testing stops; otherwise the null hypothesis  $H_{(i)}$  and testing continues at the next step. At Step 4, the null hypothesis  $H_{(4)}$  is rejected if  $p_{(4)} \leq \alpha/4$ ; otherwise  $H_{(4)}$  is accepted. The constants used in the testing procedure are defined by  $c_i = (i+1)/(2i)$  and  $d_i = 1/i$  and are given in the table below.

i	1	2	3	4
$c_i$	1	3/4	2/3	5/8
$d_i$	1	1/2	1/3	1/4

This semiparametric multiple testing procedure controls the family-wise error rate in the strong sense if the test statistics follow a multivariate normal distribution with non-negative correlation coefficients (Gou et al. 2014) which can be assumed for the investigated 4 efficacy endpoints.

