### **Dynamic mechanical allodynia**

The change from baseline in the DMA will be analyzed using a similar model as for average pain intensity. Only subjects with allodynia at baseline, i.e., a DMA score greater than 0 on the 0 to 10 NRS, will be included in the analysis.

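### Dynamic mechanical allodynia is scored as a plain geometric mean of ratings that may be 0, so one painless stroke sets the whole score to 0, which distorts a confirmatory secondary endpoint and its analysis population

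*Protocol*

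**What the plan says.** Protocol Section 12.3.2 describes the test: "The tactile stimulus is tested 5 times". Each stroke is rated from 0 to 10, with 0 meaning no pain. If the subject gives a 10, "then no further test will be performed for the respective visit", so fewer than five ratings may be available. The score is then defined: "The degree of pain sensitivity is calculated by the geometrical mean of the pain ratings given". No offset, replacement value or other rule for a rating of 0 appears in that section or wherever else the protocol deals with DMA (Sections 1.2, 1.5.3.2, 1.5.3.4, 12.9, 14.1.7.2 and 14.1.7.4).

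Sections 1.5.3.2 and 14.1.7.2 restrict the analysis: "Only subjects with allodynia at baseline, i.e., a DMA score greater than 0 on the 0 to 10 NRS" are included. The model is the one used for pain: "The change from baseline in the DMA will be analyzed using a similar model as for average pain intensity". Sections 1.5.3.4 and 14.1.7.4 place the "change from baseline to Week 12 in the pain intensity level of DMA" among the four secondary hypotheses of the confirmatory step-up procedure.

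**The concern.** The scoring formula and the rating scale do not fit together. A geometric mean is meaningful for strictly positive values, and here 0 is both permitted and likely in a subject whose allodynia is patchy or improving. One 0 overrides all the other ratings.

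Two stated rules then give wrong answers. The baseline rule treats a score of 0 as absence of allodynia, although Section 12.3.2 itself defines allodynia as pain evoked by a non-nociceptive stimulus, which a subject with four painful strokes out of five has reported. The change score treats a single painless stroke at Week 12 as full recovery. At stake are who is analysed, what the estimated difference means, and the power of one of the four confirmatory secondary tests. Because the four tests share a step-up procedure, a weaker DMA p-value can also change which of the other hypotheses are rejected.

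**Working it through.** **The plan's own figure.** The protocol states no effect, SD or sample size for DMA. Its only design calculation is for the primary endpoint (Section 1.5.1: difference 1.0, SD 2.0, one-sided 2.5%). That reproduces: with the noncentral t distribution, 85 per arm gives 89.99% power and 86 gives 90.32%. The DMA point does not depend on it.

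**What follows from the text alone.** The score is (x1 × … × xk)^(1/k), where k is the number of ratings given.

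| Ratings | As written | Arithmetic mean | Geometric mean of (x+1), minus 1 | Geometric mean of (x+0.1), minus 0.1 |
|---|---|---|---|---|
| 8,8,8,8,8 | 8.0 | 8.0 | 8.0 | 8.0 |
| 1,8,8,8,8 | 8^(4/5) = 5.28 | 6.6 | 5.66 | 5.33 |
| 0,8,8,8,8 | 0 | 6.4 | 4.80 | 3.26 |
| 0,10 (testing stops) | 0 | 5.0 | 2.32 | 0.90 |

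The offsets 1 and 0.1 are illustrations, not protocol values.

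- One rating moving from 1 to 0, with the other four at 8, lowers the score by 5.28 points.
- A subject with 0,8,8,8,8 at baseline fails the requirement of "a DMA score greater than 0 on the 0 to 10 NRS" and is not analysed. So does a subject who rates 0 and then the maximum of 10.
- A subject going from 8,8,8,8,8 to 0,8,8,8,8 has a recorded change of 0 − 8 = −8. On the arithmetic mean it is 6.4 − 8 = −1.6.

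**How often a visit would score 0 (assumed).** If each of five strokes independently has probability p of a 0, the chance of at least one is 1 − (1 − p)^5:

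| p | Visits scoring 0 |
|---|---|
| 0.02 | 9.6% |
| 0.05 | 22.6% |
| 0.10 | 41.0% |
| 0.20 | 67.2% |

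**Effect on the analysis (simulation, all inputs assumed).** 60 subjects per arm, true difference 1.0, between-subject SD 2, baseline mean 3 to 5, within-visit SD 1 to 2, and analysis of covariance at Week 12. The 60 per arm is in line with the 90 per arm planned in Section 1.5.1 and the roughly 70% with allodynia on examination quoted in Section 12.9 (0.70 × 90 = 63). Power with geometric / arithmetic scoring, 1,000 simulated trials per cell:

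| Baseline mean | Within-visit SD 1 | SD 1.5 | SD 2 |
|---|---|---|---|
| 3 | 72% / 84% | 54% / 79% | 39% / 73% |
| 4 | 82% / 88% | 67% / 83% | 50% / 76% |
| 5 | 86% / 90% | 76% / 83% | 61% / 77% |

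The loss runs from 4 points (90 − 86) to 34 points (73 − 39). In the middle cell, 21% of subjects with a painful baseline rating are excluded, 33% score 0 at Week 12 despite a painful rating, and the residual SD is 1.96 against 1.54. Adding a baseline-to-Week-12 correlation of 0.6 and a placebo change of −0.5 gives much the same: residual SD 2.03 against 1.60, power 71% to 72% against 84%. With a within-visit SD of only 0.5, the loss is about 0 to 7 points and 2% to 12% are excluded.

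**Where the power goes.** In the middle case the standardised effect falls only from 0.56 to 0.52, and the analysed sample from about 119 to 94. With power ≈ Φ(d × √(N/4) − 1.96):

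- d = 0.56, N = 119: Φ(1.09) = 86%
- d = 0.56, N = 94: Φ(0.76) = 77%
- d = 0.52, N = 94: Φ(0.56) = 71%

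So roughly 9 of the 15 points come from excluded subjects and 6 from the noisier score. Scoring also changes the estimate itself: across baseline means 3 to 5 and within-visit SDs 0.5 to 2, the unadjusted treatment difference in change was about 4% to 27% larger on the geometric scale and the SD of change about 4% to 32% larger.

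**The case against.** The strongest reply is that a zero rule may sit elsewhere. Section 12.3.2 takes the score from a cited sensory-testing publication, and Section 14.1.2 leaves full analysis details to the SAP, which is not at hand. That limits what can be said about how the analysis would in fact be run. It does not rescue the protocol text, which states both a formula and a population cut-off that fail on a valid rating. An offset introduced in the SAP would depart from that formula.

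Second, the magnitudes rest on assumptions, and five identical strokes at one visit may be rated quite consistently. This stands: the lower end of the power loss is about zero, and independence between strokes probably overstates how often zeros mix with other ratings in a subject with stable allodynia.

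Third, the exclusion uses pre-treatment data, the score is applied alike in both arms, and excluded subjects leave only this analysis. This also stands. No inflation of type I error is claimed, and the primary endpoint is untouched. DMA is tested only if the primary endpoint succeeds.

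Fourth, an unnamed offset would be arbitrary, as the 4.80 and 3.26 for the same ratings show. That is a reason to name the offset, not to leave the formula as it is.

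**Conclusion.** The concern holds. It is certain, from the protocol alone, that a single rating of 0 makes the DMA score 0, removes from the analysis a subject who reported pain on every other stroke at baseline, and records complete resolution in such a subject at Week 12. This affects a confirmatory endpoint through a stated rule, not through detail left to a later document.

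The practical size is not known from the protocol. Under the assumptions above, power falls by 4 to 34 points for within-visit SDs of 1 to 2, with about 5% to 46% of subjects who reported pain at baseline excluded. At a within-visit SD of 0.5 the loss is between nil and about 7 points. The harm is to measurement validity, the analysis population and power; type I error and the primary analysis are not affected.

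**What to change.** In Section 12.3.2, define the DMA score as the arithmetic mean of the ratings given at the visit. This matches the arithmetic mean that Section 12.3.3 already uses for the pressure pain threshold. Alternatively, keep the geometric mean but add one named constant to every rating before averaging and subtract it afterwards. In Sections 1.5.3.2 and 14.1.7.2, define allodynia at baseline as at least one rating above 0, independently of the summary score.

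In the middle simulated case, with this population rule, the options perform almost alike: power 84% with the arithmetic mean, 82% with an offset of 1 and 81% with 0.1. Naming the choice therefore matters more than which one is taken.

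The cost is a sentence in Section 12.3.2 and one in each of the two analysis sections, with no change to data collection, provided the individual ratings are kept. The one drawback is that the score no longer equals the plain geometric mean now given in the protocol. The rule must be set before unblinding, since a zero rule chosen afterwards could be driven by the data.

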#### **12.3.3 Pressure pain threshold**

The PPT is assessing the level of pressure causing deep joint or muscle pain. In CRPS subjects, light, normally non-painful pressure applied at joints or muscles causes pain in the deep somatic tissues (Baron et al. 2010). The PPT is assessed by the investigator on both affected and unaffected limbs by using a pressure algometer (contact area 1 cm^2), documented in the source data, and transferred to the eCRF. The threshold for pressure induced pain is measured on the thenar muscle/abductor hallucis muscle, starting with the unaffected limb. Measurements are repeated in 3 series of slowly increasing stimulus intensities (at a rate of about 50 kPa/s). The subject must not be able to look at the readings during the measurement. Data are averaged for the each of the 3 series of measurements. For the final PPT, the arithmetic mean of all 3 consecutive measurements is calculated (Rolle et al. 2010 and Mainka et al. 2014).

The ratio of the thresholds of the affected and the unaffected limb will be calculated.

### **12.3.4 Edema measurement**

Edema will be measured by the investigator with measurement tape using the figure-of-eight method at both the affected and contralateral unaffected limb for all subjects having edema as a positive CRPS sign at baseline (based on clinical judgment; sign “Asymmetric edema” ticked “yes” on the CRPS Severity Score at Visit 2) and will be documented in the source data and transferred to the eCRF. At each visit, first the unaffected limb has to be measured to accustom the subject to the measurements, followed by the affected limb. Each measurement of the limbs will be performed 3 times. The average of the 3 measurements will be used for further analysis.

The ratio of the averages of the affected and the unaffected limb will be calculated.

Detailed instructions and training describing in depth the figure-of-eight method for measuring edema in both hands or feet will be provided to the investigators.

### **12.3.5 Active range of motion measurement**

The AROM is the range of movement through which a subject can actively (without assistance) move a joint using the adjacent muscles. Measuring the AROM does not involve any external stimulation; the subject is not touched and decides how far to move. The magnitude of the AROM can be influenced by other factors not directly related to the joint, such as the subject’s motivation. In order to maximize the reliability of measurements, a rigid measurement protocol and valid and reliable measurement instruments were developed. Detailed instructions and in depth training will be provided to the investigators.

The subject has to be instructed not to exceed the pain limit in order to avoid increase of complaints, which could influence future measurements and treatment outcome.

For subjects having decreased AROM at baseline (diagnosed based on clinical judgment; sign “Motor abnormalities” ticked “yes”, sub-category “decreased AROM” ticked “yes” on the CRPS Severity Score at baseline [Visit 2]), both affected and unaffected limbs will be measured using a goniometer, first the unaffected extremity to accustom the patient to the measurements, followed by the affected extremity. The AROM is measured only during active flexion and extension (i.e., sagittal plane, transversal axis) of the wrist or ankle, respectively.

The AROM in each of the unaffected and affected limbs will be measured 2 times. The results of both measurements will be documented; only the best performance of the 2 repetitions will be used for further analysis.

The ratio of the AROM of the affected and the unaffected limb will be calculated.

### **12.3.6 CRPS Severity Score**

Signs and symptoms of CRPS (Section 18.4) will be assessed by the investigator and recorded using the tablet computers maintained at the sites. Subjects will be queried on 8 self-reported symptoms (queried yes or no): continuous, disproportionate pain; allodynia and/or hyperalgesia; temperature asymmetry; color asymmetry; sweating asymmetry; edema; dystrophic changes; and motor abnormalities. Symptoms will be assessed based on a recall period of 48 hours. Subjects will be examined for 8 signs (observed on examination, yes or no): hyperalgesia to pinprick; allodynia; temperature asymmetry by palpation; skin color asymmetry; sweating asymmetry; asymmetric edema; dystrophic changes; and motor changes (please refer to Section 12.2.3.1 and Section 18.4

for the description of the signs and symptoms). Each sign or symptom is assigned a dichotomous value (1 = presence; 0 = absence). The resulting score ranges from 0 to 16, with higher scores indicating greater CRPS severity (Harden et al. 2010b).

### **12.3.7      Patient Global Impression of Change**

The PGIC will be assessed using the tablet computers maintained at the sites. The 7-point PGIC is a complementary assessment of analgesic efficacy. Subjects respond to the question “Since the start of the trial, my overall status is:” with 1 of 7 possible responses (very much improved, much improved, minimally improved, no change, minimally worse, much worse, very much worse; Section 18.3.1). A response of very much improved or much improved is generally regarded as a clinically important outcome. As “change” is conceptually inherent in the questionnaire, no baseline assessment can be performed.

### **12.3.8      Patient Global Impression of Severity**

The PGI-S will be assessed by the subjects using the tablet computers maintained at the sites. The 5-point PGI-S is a 1-item questionnaire designed to assess a patient’s impression of disease severity.

Subjects are asked to best describe their CRPS symptoms over the past week with 1 of 5 possible responses (none, mild, moderate, severe, very severe; Section 18.3.2).

### **12.3.9      EuroQoL-5 dimension-5 level**

The EQ-5D-5L health questionnaire (Section 18.3.3) will be completed by all subjects using the tablet computers maintained at the sites. The EQ-5D-5L has 5 dimensions: mobility, self-care, usual activities, pain/discomfort, and anxiety/depression. Each of the 5 dimensions has 5 possible levels: no problems, slight problems, moderate problems, severe problems, and extreme problems. An index (total) score will be calculated from data from all 5 dimensions using an index value calculator that can be downloaded from the EuroQol website. For the US general population, the possible EQ-5D-5L index scores range from -0.109 (i.e., 55555) to 1.0 (i.e., 11111) on a scale where 0.0 = death and 1.0 = perfect health. The EQ-VAS ranges from 0 (worst imaginable health) to 100 (best imaginable health). A higher score represents better overall health.

### **12.3.10     PROMIS-29 profile and the PROMIS-EDDEP39**

The PROMIS-29 profile (Section 18.3.4) assesses 7 domains, i.e., depression, anxiety, physical function, pain interference, fatigue, sleep disturbance, and ability to participate in social roles and activities, each with 4 questions and a recall period of 7 days (Cella et al. 2007).

The PROMIS-29 Profile version 2.0 will be completed by the subjects using the tablet computers maintained at the sites.

In addition, suicidal ideation will be assessed using the PROMIS-EDDEP39 (Section 18.3.5), which is Question EDDEP39 of the PROMIS Item Bank version 1.0 – Emotional Distress – Depression (Pilkonis et al. 2011).

### **12.3.11      Short-Form McGill Pain Questionnaire 2: 6 neuropathic pain items**

The SF-MPQ-2 is a single measure of the major symptoms of both neuropathic and non-neuropathic pain. The pain qualities will be assessed using the 6 neuropathic items from the SF-MPQ-2 (Section 18.3.6).

Subjects will be asked to consider and report only the pain related to the CRPS when completing the instrument using the tablet computers maintained at the sites.

### **12.3.12      Pain Catastrophizing Scale**

The PCS (Section 18.3.7) will be used as a measurement tool to capture pain catastrophizing; the scale will be completed by the subjects using the tablet computers maintained at the sites.

### **12.3.13      Pain Self Efficacy Questionnaire**

The PSEQ (Section 18.3.8) will be used to capture pain self-efficacy and is completed by the subjects using the tablet computers maintained at the sites.

## **12.4      Collection of safety data**

The following safety data will be collected: adverse events, vital signs, 12-lead ECGs, safety laboratory parameters, physical examination findings, and urine  $\beta$ -HCG pregnancy test outcome.

For the timings of assessments, see the schedules of events (Section 1.6).

Clinically relevant abnormal values (investigator's judgment) must be recorded as adverse events.

### **12.4.1      Adverse events**

Adverse events will be documented from the time of enrollment (i.e., the time the informed consent form is signed) up to the time of the last protocol scheduled contact, i.e., date of last visit/contact (can be a phone call, e.g., in case of withdrawal).

#### **Definition of adverse events**

An adverse event is any untoward medical occurrence in a subject enrolled in a clinical trial. An adverse event can therefore be any unfavorable and unintended sign (e.g., an abnormal laboratory finding), symptom, or disease temporally associated with the use of a medicinal product, whether or not considered related to the medicinal product.

Pre-existing diseases or conditions occurring before enrollment are not considered to be adverse events unless there is an untoward change in intensity, frequency, or quality after enrollment.

Lack of efficacy, as such, is not considered to be an adverse event while its consequences (e.g., deterioration of the treated disease) are considered to be an adverse event.

A newly diagnosed pregnancy of an enrolled female subject will not be considered an adverse event itself unless it is suspected that the trial treatment interacted with a contraceptive method. In this case, the pregnancy will be considered an adverse event. A congenital anomaly as an outcome of a pregnancy will be considered a serious adverse event (SAE).

All newly diagnosed pregnancies of enrolled female subjects must be reported to the sponsor's Drug Safety Department within 24 hours after first knowledge. These pregnancies will be

documented using a pregnancy reporting form with all available information provided and followed up to determine the outcome post parturition.

For newly diagnosed pregnancies of partners of enrolled subjects, a reasonable attempt (i.e., due diligence) must be made to report the pregnancy to the sponsor's Drug Safety Department within 24 hours after first knowledge.

